6.5.4.2 Anaphylaxis

Anaphylaxis should lead to immediate interruption of ongoing infusion, and to permanent discontinuation of SAR444245, pembrolizumab and cetuximab being administered.

Management should be prompt and may include but is not limited to administration of epinephrine, IV fluids, antihistamines, oxygen, vasopressors, corticosteroids, as well as increased monitoring of vital signs as medically indicated, until the participant recovers (see guidelines) ([36](#), [1](#), [37](#)).

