6.5.4.1 Infusion-related reactions (IRR)

Participants should routinely receive premedication as detailed in Section 6.1.2.1 of the master protocol prior to SAR444245 administration, to prevent or reduce the incidence or severity of IRRs.

An infusion-related reaction in this study is defined as any signs or symptoms which develop during the infusion or up to 24 hours after the completion of the infusion. The term IRR indicates only a specific temporal relationship with the infusion and does not specify a particular mechanism underlying the signs or symptoms.

Pembrolizumab may cause severe or life-threatening infusion-reactions including severe hypersensitivity or anaphylaxis. Signs and symptoms usually develop during or shortly after drug infusion and generally resolve completely within 24 hours of completion of infusion. Dose modification and toxicity management guidelines on pembrolizumab-associated infusion reaction are provided in [Table 5](#).

After an infusion-related reaction due to pembrolizumab infusion (Grade 3 or Grade 4), the SAR444245 infusion will be delayed and can be administered after resolution of symptoms. The Investigator should discuss with the Sponsor's Medical Monitor if the SAR444245 infusion needs to be delayed more than 1 day.

Guidelines for the management of SAR444245 IRR events are provided in [Table 6](#). Participants who develop Grade 2 IRR should have the next SAR444245 infusion given at half the infusion rate. For instructions on premedication at subsequent dosing, please see Section 6.1.2.1 of the master protocol.

Table 5 - Pembrolizumab infusion-related reaction dose modification and treatment guidelines

NCI CTCAE Grade	Treatment	Premedication at subsequent dosing
Grade 1 Mild transient reaction; infusion interruption not indicated; intervention not indicated	
 • Increase monitoring of vital signs as medically indicated until the participant is deemed medically stable in the opinion of the investigator. 	None

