Grade 3 Prolonged (ie, not rapidly responsive to symptomatic medication and/or brief interruption of infusion); recurrence of symptoms following initial improvement; hospitalization indicated for other clinical sequelae	SAR444245 infusion should be interrupted if applicable. If IRR is clearly attributable to SAR444245, SAR444245 should be permanently discontinued. The participant can continue treatment with the other anti-cancer therapy in combination During or after completion of infusion, additional appropriate medical therapy may include but is not limited to epinephrine ^b , IV fluids, antihistamines, NSAIDs, acetaminophen, narcotics, oxygen, vasopressors, corticosteroids. Increase monitoring of vital signs as medically indicated until the participant recovers.
Grade 4 Life-threatening; pressor or ventilator support indicated	SAR444245 infusion should be interrupted if applicable. If IRR is clearly attributable to SAR444245, SAR444245 should be permanently discontinued. The participant can continue treatment with the other anti-cancer therapy in combination During or after completion of infusion, additional appropriate medical therapy may include but is not limited to epinephrine ^b , IV fluids, antihistamines, NSAIDs, acetaminophen, narcotics, oxygen, vasopressors, corticosteroids. Increase monitoring of vital signs as medically indicated until the participant recovers.

a Information for preparation and storage of SAR444245 are provided in the pharmacy manual.

b In cases of anaphylaxis, epinephrine should be used immediately

Abbreviations: CTCAE = Common terminology criteria for adverse events; IRR = Infusion-related reaction; NCI = National Cancer Institute; NSAIDs: nonsteroidal anti-inflammatory drugs.

Participants who experience cetuximab-related infusion reactions should have cetuximab reduced according to [Table 7](#) and continue to receive antihistamine premedication prior to administration. Once the cetuximab infusion rate has been decreased due to an allergic/hypersensitivity reaction, it should remain decreased for all subsequent infusions. If the participant experiences a second infusion reaction at the decreased rate, cetuximab should be permanently discontinued. If any Grade 3-4 infusion reaction occurs, cetuximab treatment should be discontinued immediately.

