Severe infusion-related reactions, including anaphylactic reactions, may commonly occur, in some cases with fatal outcome. Occurrence of a severe infusion-related reaction requires immediate and permanent discontinuation of cetuximab therapy and may necessitate emergency treatment. Some of these reactions may be anaphylactic or anaphylactoid in nature or represent a cytokine release syndrome (CRS). Symptoms may occur during the first infusion and for up to several hours afterwards or with subsequent infusions.

Table 7 - Cetuximab infusion-related reaction dose modification and treatment guidelines

NCI CTCAE Grade	Dose modification
Grade 1 Mild reaction; infusion interruption not indicated; intervention not indicated	Decrease the cetuximab infusion rate by 50% and monitor closely for any worsening.
Grade 2 Requires therapy or infusion interruption but responds promptly to symptomatic treatment (eg, antihistamines, NSAIDs, narcotics, IV fluids); prophylactic medications indicated for ≤24 hrs	Stop cetuximab infusion and administer bronchodilators, oxygen, etc. as medically indicated. Resume infusion at 50% of previous rate once allergic/hypersensitivity reaction has resolved or decreased to Grade 1 in severity and monitor closely for any worsening.
Grades 3 or 4 Grade 3: Prolonged (ie, not rapidly responsive to symptomatic medication and/or brief interruption of infusion); recurrence of symptoms following initial improvement; hospitalization indicated for other clinical sequelae (eg, renal impairment, pulmonary infiltrates) Grade 4: Life-threatening; pressor or ventilator support indicated	Stop the cetuximab infusion immediately, administer epinephrine, bronchodilators, antihistamines, glucocorticoids, intravenous fluids, vasopressor agents, oxygen, etc., as medically indicated. Cetuximab should permanently discontinued. The participant can continue treatment with SAR444245.

Abbreviations: CTCAE = Common terminology criteria for adverse events; IRR = Infusion related reaction; NCI = National Cancer Institute.

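### Section 6.5.4.2 stops every study drug after anaphylaxis, but the Grade 3-4 infusion-reaction guidance in Section 6.5.4.1 lets the partner drug go on without excepting anaphylaxis

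*Protocol*

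**What the plan says.** **The anaphylaxis rule.** Section 6.5.4.2 of substudy 04 reads: "Anaphylaxis should lead to immediate interruption of ongoing infusion, and to permanent discontinuation of SAR444245, pembrolizumab and cetuximab being administered". The same section in substudies 02 and 03 applies the rule to both SAR444245 and pembrolizumab.

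**The infusion-reaction guidance in Section 6.5.4.1.**

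- An infusion-related reaction "is defined as any signs or symptoms which develop during the infusion or up to 24 hours after the completion of the infusion". The section adds that the term describes timing only and implies no mechanism.
- SAR444245 reactions are covered by Table 4 (substudies 02 and 03) and Table 6 (substudy 04). At Grades 3 and 4, SAR444245 is permanently stopped if the reaction is clearly put down to it, and "The participant can continue treatment with the other anti-cancer therapy in combination". Footnote b of these tables says "In cases of anaphylaxis, epinephrine should be used immediately" and nothing about discontinuation.
- Cetuximab reactions are covered by Table 7 (substudy 04). At Grades 3 or 4 cetuximab is stopped for good, and "The participant can continue treatment with SAR444245". The paragraph above the table says "Severe infusion-related reactions, including anaphylactic reactions, may commonly occur, in some cases with fatal outcome". It goes on: "Some of these reactions may be anaphylactic or anaphylactoid in nature or represent a cytokine release syndrome (CRS").
- In all three substudies, after a Grade 3 or 4 pembrolizumab reaction "the SAR444245 infusion will be delayed and can be administered after resolution of symptoms". The sponsor's medical monitor is to be consulted only if that delay exceeds one day.
- The pembrolizumab tables (Table 3 in substudies 02 and 03, Table 5 in substudy 04) carry the same epinephrine footnote, followed by a line that permanently ends further study drug treatment.

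**The concern.** An anaphylactic reaction during or soon after an infusion is also an infusion-related reaction under the protocol's definition, and if severe it will be graded 3 or 4. A site that looks it up in the grading table is told the partner drug may continue. A site that turns to Section 6.5.4.2 is told that all the drugs should stop permanently.

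At stake is re-exposure to a study drug after a life-threatening event. After a pembrolizumab reaction, the running text would allow SAR444245 within a day without contacting the sponsor. In Cohort D2 the exposure would often be new. The substudy 04 synopsis gives SAR444245 after cetuximab only if no reaction is reported in the observation period, so a participant with anaphylaxis on the first cetuximab dose would usually not yet have had SAR444245. Section 2.3.1.2 of that substudy lists anaphylaxis on the first dose among the important identified risks of cetuximab.

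**Working it through.** No statistical figure is involved, so the check compares the instructions and then counts how far the wording reaches.

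**Side by side**

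| Event | Section 6.5.4.2 | Section 6.5.4.1 | Anaphylaxis excepted in 6.5.4.1? |
|---|---|---|---|
| Grade 3-4 reaction to cetuximab (substudy 04) | Stop all study drugs | Table 7: stop cetuximab; SAR444245 may continue | No |
| Grade 3-4 reaction to SAR444245 (all three substudies) | Stop all study drugs | Tables 4 and 6: stop SAR444245 if clearly the cause; partner may continue | No; footnote b covers epinephrine only |
| Grade 3-4 reaction to pembrolizumab (all three substudies) | Stop all study drugs | Running text: delay SAR444245, then give it | No |
| Same event, pembrolizumab tables 3 and 5 | Stop all study drugs | Further study drug treatment ends | Not needed; agrees with 6.5.4.2 |

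**Does anaphylaxis fall inside the cells?**

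- Table 7: yes, on the document's own words, because the lead-in says these reactions may be anaphylactic.
- Tables 4 and 6: yes, by inference. The definition rests on timing alone, and the anaphylaxis footnote is called from within the Grade 3 and 4 cells.
- Running text: the paragraph just before the sentence names anaphylaxis as a possible pembrolizumab reaction.

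**Does another rule settle it?**

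- The Section 6.5.1 clause that favours the most conservative recommendation is written for a participant with several toxicities. Here there is one toxicity under two rules.
- Section 6.5.1 also says that when one component is permanently stopped the other can go on until progression or other criteria in master protocol Section 7.1.1. That default favours continuing.
- In Table 15 of substudy 04, the hypersensitivity and anaphylaxis row sends the cetuximab reader to the infusion-reaction row. The Grade 3-4 action there rules out further cetuximab and does not tell the site to stop SAR444245.

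**Reach of the wording**

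- Cells: Table 4 substudy 02 (2) + Table 4 substudy 03 (2) + Table 6 (2) + Table 7 (1, grades combined) = 7.
- Sentences on SAR444245 after a pembrolizumab reaction: one in each of three substudies = 3.
- Planned participants, from Section 9.2 of each substudy: Cohorts B1, B2, B3, C, D1 and D2, 6 × 40 = 240, all under the SAR444245 tables.
- Under the pembrolizumab sentence: B1, B2, B3, C and D1, 5 × 40 = 200.
- Under Table 7: D2, 40.

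These are numbers of participants governed by the wording, not expected cases. Section 2.3.1.2 of substudy 04 gives 2.2% for all Grade 3 and 4 cetuximab infusion reactions, which is not an anaphylaxis rate and is not used here.

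**The case against.** The best defence is that the rules can be read together. The tables give general guidance by grade; anaphylaxis has its own heading immediately after them, and a specific section can be taken to prevail. The tables only permit continuation, so a site that stops everything breaks no cell. Section 6.5.3 leaves the final decision on dose modification to the investigator. For pembrolizumab, the tables in the same subsection already end study treatment. In D2, Table 15 bars starting SAR444245 if a reaction has occurred during the observation period. Master protocol Section 7.1.1, which limits continuation of the remaining drug, was not available and might list anaphylaxis.

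Much of this is fair and limits the weight of the point. In Tables 4 and 6 the conflict is an inference from the definition and a footnote. The comparison with the pembrolizumab tables also depends on reading their discontinuation line as part of the anaphylaxis footnote, which the extracted layout does not settle.

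It does not remove the conflict. No statement of precedence appears in the text at hand, and the tables' Grade 3-4 cells do not point to Section 6.5.4.2. Investigator discretion does not make two opposite instructions consistent. The Table 15 bar concerns giving SAR444245 after that observation period, not later cycles. The gap in Table 7 stands on the document's own wording.

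**Conclusion.** The concern holds. Section 6.5.4.1 permits continued dosing, after a Grade 3-4 reaction that may be anaphylaxis, with a drug that Section 6.5.4.2 says should be permanently stopped. The case is strongest for Table 7, good for Tables 4 and 6, and weakest for the pembrolizumab sentence, because the adjoining tables point the other way.

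Few participants would be affected, and no rate can be given. The wording governs about 240 planned participants, and each affected case could be serious. No estimate, test or sample size changes. The conclusion assumes that master protocol Section 7.1.1 does not already require all drugs to stop after anaphylaxis. Even if it does, the cells should say so where sites will look. The change should be made at the next amendment.

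**What to change.** At the next amendment:

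1. In the Grade 3 and 4 cells of Table 4 (substudies 02 and 03) and Table 6 (substudy 04), and in the Grades 3 or 4 cell of Table 7 (substudy 04), add beside the permission to continue the other drug: *except anaphylaxis: permanently discontinue all study drugs, see Section 6.5.4.2*.
2. In Tables 4 and 6, attach the same exception to the attribution condition, so that stopping SAR444245 after anaphylaxis does not depend on a judgement of cause.
3. Add the same exception to the Section 6.5.4.1 sentence on giving SAR444245 after a Grade 3-4 pembrolizumab reaction, in all three substudies.
4. Optionally, add a cross-reference to Section 6.5.4.2 in the hypersensitivity row of Table 15 (substudy 04).

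The cost is one phrase in seven cells of four tables and in three sentences. No procedure, visit or patient is added.

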6.5.4.3 Fever, flu-like symptoms and cytokine-release syndrome (CRS)

Fever can frequently happen with infusion of IL-2 and may possibly evolve into flu-like symptoms or could be an early manifestation of CRS. Fever or flu-like symptoms should be graded according to CTCAE V5.0 and managed according to institutional standards.

Cetuximab may be associated with CRS. CRS typically occurs within one hour after infusion and is less commonly associated with bronchospasm and urticaria. CRS is normally most severe in relation to the first infusion of cetuximab. Cetuximab related IRR's, including CRS, are discussed in [Section 6.5.4.1](#). Please refer to [Table 7](#) for Cetuximab IRR dose modifications and treatment guidelines.

Cytokine-release syndrome should be graded as per American Society for Transplantation and Cellular Therapy (ASTCT) criteria integrated with central laboratory cytokine results, and managed per guidelines in [Table 8](#). If any grade of CRS is suspected, sites should make every effort to draw an additional blood sample for cytokines levels (by central laboratory) prior to the administration of tocilizumab, as well as C-reactive protein (CRP) and ferritin (by local laboratory).

Sites should have at least 2 full doses of tocilizumab available and access to an intensive care unit (ICU), in case participants develop CRS.

Guidelines for management of CRS according to severity grading are provided in [Table 8](#). ASTCT CRS consensus grading scale is provided in Section 10.11 of the master protocol.

Table 8 - Guidelines for the management of suspected cytokine release syndrome (CRS)

Event severity (ASTCT CRS Consensus Grading)	Recommended SAR444245 dose modification and supportive care guidelines	Recommended Cetuximab dose modifications and supportive care guidelines
Grade 1 
• Fever (Temperature $\geq 38^{\circ}\text{C}$)^b• No hypotension• No hypoxia	
No dose modification of SAR444245^a
 
Appropriate symptomatic treatment may include but is not limited to IV fluids (care should be taken to not excessively hydrate if evidence of vascular leak), antihistamines, NSAIDs and acetaminophen.
 
Close direct monitoring of the participant's clinical status. Clinical and laboratory monitoring should initially be performed daily, then less frequently as the participant improves.
	Decrease the cetuximab infusion rate by 50% and monitor closely for any worsening.

Event severity (ASTCT CRS Consensus Grading)	Recommended SAR444245 dose modification and supportive care guidelines	Recommended Cetuximab dose modifications and supportive care guidelines
Grade 2	
 Fever^b (Temperature $\geq 38^{\circ}\text{C}$) Hypotension not requiring vasopressors and/or^c hypoxia requiring low-flow nasal cannula^d or blow-by. 
Temporarily interrupt SAR444245 if event occurs during infusion Additional appropriate medical therapy may include but is not limited to IV fluids (care should be taken to not excessively hydrate if evidence of vascular leak), antihistamines, NSAIDs and acetaminophen. Monitoring of vital signs, cardiac and other organ functions closely as medically indicated should be increased until the participant recovers. Transfer to ICU may be required. For participants with comorbidities, older age, or with oxygen requirement, hypotension, or participants in whom symptoms (eg, high grade fever) that do not respond to antipyretics within 72 hours treatment with corticosteroids and/or tocilizumab should be considered, as per guidance for Grade 3 events.
 
SAR444245 may be resumed when clinical symptoms have resolved or improved to Grade 1 and corticosteroid taper. No dose modification is required but decreasing to half the infusion rate can be considered.
	
Stop cetuximab infusion and administer bronchodilators, oxygen, etc., as medically indicated.
 
Resume infusion at 50% of previous rate once allergic/hypersensitivity reaction has resolved or decreased to Grade 1 in severity and monitor closely for any worsening.

Grade 3	
 Fever^b (Temperature $\geq 38^{\circ}\text{C}$) Hypotension requiring a vasopressor with or without vasopressin And/or^c hypoxia requiring high-flow nasal cannula^d, face mask, nonrebreather mask, or Venturi mask 
If CRS grade 3, SAR444245 should be temporarily cycle delayed, and subsequent treatment should be resumed only when symptoms have resolved or improved to Grade 1 at $\leq 10 \mu\text{g}/\text{kg}$ or permanently discontinued, as clinically indicated. If CRS Grade 4, SAR444245 should be permanently discontinued, as clinically indicated.
 
If CRS Grade 3 or Grade 4, IV corticosteroids should be initiated (outside of the context of CAR-T cells, corticosteroids alone maybe initiated in first intention) and tocilizumab considered, and/or epinephrine and/or other vasopressors should be administered as needed.
	
Stop the cetuximab infusion immediately, administer epinephrine, bronchodilators, antihistamines, glucocorticoids, intravenous fluids, vasopressor agents, oxygen, etc., as medically indicated.

Grade 4	Life-threatening consequences; urgent intervention indicated	
Participants with severe CRS may require management in intensive care setting, with monitoring of clinical status and laboratory tests performed at least daily.
 
As the participant improves, the intensity of the monitoring and setting can be decreased, but the participant should not be discharged from the hospital until clinically stable. Corticosteroids can then be administered IV or orally every 8 hours for up to 3 days, then tapered over 4 days. In general, tapering of steroids can start when vasopressors and high-flow oxygen are no longer needed.
 
CRS is considered resolved when there is sustained resolution of fever and there is no longer a need for oxygen supplementation to relieve hypoxia nor vasopressors to maintain blood pressure; however, normalization of temperature alone does not define resolution of CRS.

Event severity (ASTCT CRS Consensus Grading)	Recommended SAR444245 dose modification and supportive care guidelines	Recommended Cetuximab dose modifications and supportive care guidelines
	
If no clinical improvement in oxygenation, hypotension, fever, and other CRS manifestations is observed within 24 to 72 hours, management for persistent or worsening CRS should be initiated. Re-evaluation for other contributing conditions should be done, such as infection, cardiac, thromboembolic and other complications. Intravenous Tocilizumab at 8 mg/kg (for participants weighing ≥ 30 kg) should be administered, and steroids should be administered concurrently. If still no improvement in oxygenation, hypotension fever and other manifestations is observed after the first dose of tocilizumab, it may be repeated after an interval of at least 8 hours and should not exceed 4 doses in total.
 
For participants with severe CRS who fail to improve after repetitive treatment with both tocilizumab and steroids, alternative options should be discussed with clinical site specialists
	

- a Information for preparation and storage of SAR444245 is provided in the pharmacy manual.
- b Fever is defined as temperature $\geq 38^{\circ}\text{C}$ not attributable to any other cause. In patients who have CRS then receive antipyretic or anticytokine therapy such as tocilizumab or steroids, fever is no longer required to grade subsequent CRS severity. In this case, CRS grading is driven by hypotension and/or hypoxia.
- c CRS grade is determined by the more severe event: hypotension or hypoxia not attributable to any other cause. For example, a patient with temperature of 39.5°C , hypotension requiring 1 vasopressor, and hypoxia requiring low-flow nasal cannula is classified as Grade 3 CRS.
- d Low-flow nasal cannula is defined as oxygen delivered at ≤ 6 L/minute. Low flow also includes blow-by oxygen delivery, sometimes used in pediatrics. High-flow nasal cannula is defined as oxygen delivered at > 6 L/minute.

Abbreviations: AE = Adverse event; ASTCT=American Society for Transplantation and Cellular Therapy; BiPAP= Bilevel Positive Airway Pressure; CPAP= Continuous Positive Airway Pressure; CRS= cytokine release syndrome; ICU=intensive care unit; IL = Interleukin; IMP=investigational medicinal product; IV = Intravenous; NSAIDs=Non-steroidal anti-inflammatory drugs.

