- c Observation Period: Participants who enter the Observation period will be followed differently depending on the reason leading to permanent IMP discontinuation. See [Section 4.1](#). For participant's convenience, all Follow-up assessments may occur during the same visit as that when tumor assessment is performed.
- d Survival Phone Call Follow-Up Period: Once the participant stops the tumor assessments due to PD or starts a new antineoplastic therapy, the participant moves into the Survival Follow-up Period and should be contacted by telephone approximately every 3 months \pm 14 days to assess for survival status. Updated survival status may be requested by the Sponsor at any time during the study.
- e For Cycle 4 visits, please refer to PK flowchart in [Section 1.5](#).
- f C1D8 and/or C1D15 visits must be performed on site for the following participants only: 1) Participants scheduled to have blood draws for biomarker assessment and/or ADA on Day 8; 2) Participants who will receive IMP on Day 8 and Day 15. For all other participants, these 2 on-site visits may be done remotely as appropriate based on investigator's discretion per institutional standard and local regulations. If this is the case, this must be documented in the source document. Sponsor may decide to cancel safety assessment on C1D8 and C1D15 if safety data justifies it.
- g Weight/Height: Height is required at baseline only. Weight is required at Screening and prior to starting each infusion. The total dose will be calculated based on the weight on the day of the infusion or the most recent weight assuming it was assessed in a reasonable time frame according to Investigator assessment. Study sites should make every effort to measure body weight as close to the infusion day as possible considering the variability of local process from site to site. If the infusion is prepared with the most recent weight assessed in a reasonable time frame, this will not prevent to assess the weight on D1 of each cycle.
- h For participants with known HIV, hepatitis B and hepatitis C infection under antiviral treatment to confirm controlled infection, and for all participants in Germany and Italy (see details and specific instructions in Section 10.2 and Section 10.7 of the master protocol).

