6.5.4.5 Immune Cell-Associated Neurotoxicity Syndrome (ICANS)

Immune cell-associated neurotoxicity syndrome (ICANS) is a neuropsychiatric syndrome which is frequently associated with CRS; however, it is specifically excluded from the definition of CRS and can occur during the course of CRS, after its resolution, or independently from CRS. Clinical findings can be progressive and may include aphasia, altered level of consciousness, impairment of cognitive skills, motor weakness, seizure, and cerebral edema. Severity is evaluated using the ASTCT Consensus grading scale, with ICE score for encephalopathy assessment (Section 10.11 of the master protocol). Recommendations for ICANS management mainly include the use of steroids, whereas tocilizumab should only be used in the context of CRS, as outlined in [Table 10](#). The proposed management should be considered only as recommendations and in light of recommendations from site specialist.

Table 10 - Guidelines for the management of immune Cell-Associated Neurotoxicity Syndrome (ICANS)

Event severity (ASTCT Consensus Grading criteria)	Recommended SAR444245 dose modification and supportive care guidelines
Mild Grade 1 ICE score 7-9. Awakens spontaneously	No intervention required other than close clinical monitoring.
Moderate Grade 2 ICE score 3-6. Awakens to voice.	SAR444245^a should be delayed. Treatment with IV corticosteroids should be initiated as needed. SAR444245 may be resumed only after participant recovery or improvement to Grade 1 after corticosteroid taper. Consideration for reduction of SAR444245 dose to █ µg/kg as per Investigator with Sponsor consultation.
Severe or Life-threatening Grade 3 ICE score 0-2. Awakens only to tactile stimulus. Any clinical seizure focal or generalized that resolves rapidly or nonconvulsive seizures on EEG that resolve with intervention.	If Grade 3 ICANS, SAR444245 should be delayed. When symptoms have resolved or improved to Grade 1 after corticosteroid taper, SAR444245 can be either restarted at █ µg/kg or permanently discontinued, as clinically indicated, and upon discussions between the Investigator and Sponsor.

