Grade 4 ICE score: 0 (participant is unarousable and unable to perform ICE). Participant is unarousable or requires vigorous or repetitive tactile stimuli to arouse. Stupor or coma. Life-threatening prolonged seizure (>5 min): or Repetitive clinical or electrical seizures without return to baseline in between. Deep focal motor weakness such as hemiparesis or paraparesis. Diffuse cerebral edema on neuroimaging; decerebrate or decorticate posturing; or cranial nerve VI palsy; or papilledema; or Cushing's triad.	If Grade 4 ICANS, both SAR444245 and pembrolizumab should be permanently discontinued. Treatment with IV corticosteroids should be initiated. Concomitant CRS may require tocilizumab and should be handled as described in Table 8 in Section 6.5.4.3 . Corticosteroids can then be administered IV or orally every 8 hours for up to 3 days, then tapered over 4 days. For both Grade 3 and Grade 4 ICANS If there is no clinical improvement within 24 to 72 hours, then re-evaluation for other contributing conditions should be done. Administration of IV Tocilizumab at 8 mg/kg (for participants weighing ≥30 kg, total dose should not exceed 800 mg) should be considered, and steroids should be administered concurrently and repeated as previously mentioned for CRS. Neurologist and other relevant clinical specialists should be involved whenever indicated.

^a Information for preparation and storage of SAR444245 is provided in the pharmacy manual

Abbreviations: ASTCT=American Society for Transplantation and Cellular Therapy; CRS= cytokine release syndrome; ICANS= Immune effector cell associated neurotoxicity syndrome; ICE= Immune Effector Cell-Associated Encephalopathy; IV = Intravenous.

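### Substudy 04: the CRS table doses tocilizumab at 8 mg/kg with no mg maximum, while the ICANS table caps the same dose at 800 mg, so the two differ above 100 kg

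*Protocol*

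**What the plan says.** Substudy 04 gives a tocilizumab dose in two places.

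- **Section 6.5.4.3, Table 8 (CRS).** If CRS has not improved within 24 to 72 hours, the site should give "Intravenous Tocilizumab at 8 mg/kg (for participants weighing" at least 30 kg). If there is still no improvement after the first dose, "it may be repeated after an interval of at least 8 hours and should not exceed 4 doses in total". The table limits the number of doses and the interval between them. Neither the table nor its footnotes limit the mg per dose.
- **Section 6.5.4.5, Table 10 (ICANS, Grades 3 and 4).** Where there is no improvement over the same period: "Administration of IV Tocilizumab at 8 mg/kg (for participants weighing ≥30 kg, total dose should not exceed 800 mg) should be considered".

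Two statements in section 6.5.4.5 tie the tables together. The introductory text says that steroids are the main treatment for ICANS, "whereas tocilizumab should only be used in the context of CRS". Table 10 itself says: "Concomitant CRS may require tocilizumab and should be handled as described in Table 8".

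**The concern.** The two tables give the same drug at the same mg/kg dose under the same lower weight condition, but only one has a ceiling. They cannot be treated as separate situations. Tocilizumab is reserved for CRS, so a participant who receives it under the capped ICANS table also falls under the uncapped CRS table, and the cross-reference sends the site there. The uncapped instruction is also the firmer of the two: Table 8 says the drug should be given, whereas Table 10 says it should be considered.

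What is at stake is participant safety. A heavy participant with severe CRS, with or without ICANS, could be given more per infusion than the protocol's own ceiling. Section 6.5.4.3 also requires sites to stock at least two full doses, and above 100 kg the size of a full dose depends on which table is read. Sample size, error rates and the response-rate analysis are not affected.

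**Working it through.** **Inputs**

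- Table 8: 8 mg/kg, at least 30 kg, no mg maximum, at most 4 doses.
- Table 10: 8 mg/kg, at least 30 kg, maximum 800 mg.
- Section 9.2: about 40 participants in each of Cohorts D1 and D2, so 2 × 40 = 80.

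**Meaning of the cap.** Table 10 limits the *total dose*. Elsewhere the protocol uses that term for the amount of one weight-based infusion (section 1.3, footnote g: "The total dose will be calculated based on the weight on the day of the infusion"). The 800 mg is therefore read as a limit per infusion.

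**Dose per infusion**

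- Table 8: dose = 8 × weight.
- Table 10: dose = min(8 × weight, 800).
- The two part at weight = 800/8 = 100 kg.

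| Weight (kg) | Table 8 (mg) | Table 10 (mg) | Excess |
|---|---|---|---|
| 70 | 560 | 560 | 0 |
| 100 | 800 | 800 | 0 |
| 110 | 880 | 800 | 80 (+10%) |
| 120 | 960 | 800 | 160 (+20%) |
| 140 | 1120 | 800 | 320 (+40%) |

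Over the four permitted doses at 120 kg: 4 × 960 = 3840 mg uncapped, against 4 × 800 = 3200 mg with a per-infusion cap. The two-dose stock at 120 kg is 2 × 960 = 1920 mg or 2 × 800 = 1600 mg.

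**If the cap were cumulative.** Two doses of 8 mg/kg pass 800 mg above 800/16 = 50 kg, and four doses pass it above 800/32 = 25 kg. Since Table 8 allows four doses, the disagreement would be wider.

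**How many participants might be affected.** The protocol gives neither a weight distribution nor a rescue rate, so both are assumed here.

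- Weight Normal(70, 15): z = (100 − 70)/15 = 2.00, so P(weight > 100) = 0.0228 and 80 × 0.0228 = 1.8 participants.
- Weight Normal(80, 18): z = (100 − 80)/18 = 1.11, so P(weight > 100) = 0.1333 and 80 × 0.1333 = 10.7 participants.
- If 1% to 5% of participants reach tocilizumab rescue, independently of weight: 80 × 0.0228 × 0.01 = 0.018 at the low end and 80 × 0.1333 × 0.05 = 0.53 at the high end.

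**After the fix.** With a maximum of 800 mg per infusion in both tables, each gives min(8 × weight, 800). The difference is 0 mg at every weight from 30 kg up.

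**The case against.** The strongest reply is that the point rests on words that are absent, and that they may be absent for other reasons.

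- **Incomplete text.** The text of Table 8 available for this check lacks Grade 4 CRS criteria that the parallel Table 5 of Substudy 02 contains, so a cap could also have dropped out. This cannot be excluded. However, the tocilizumab sentence is complete, its bracket closes after the weight condition, and the damage lies elsewhere in the table.
- **Master protocol.** Section 6.1.4 refers readiness for severe CRS to the master protocol, which was not available and may state a general maximum. That uncertainty stands. For CRS itself, though, section 6.5.4.3 cites the master protocol only for the grading scale and sends management to Table 8. A cap stated elsewhere would not make the two tables agree.
- **Silence is not contradiction.** A site that stops at 800 mg breaks no ceiling in Table 8. That is true, but a site that follows Table 8 as written exceeds the ceiling in Table 10.
- **Guidance only.** Both tables are guidelines, section 6.5.4.5 calls the ICANS advice recommendations, and section 6.5.3 leaves corrective therapy to the investigator's judgment. This limits the consequence. It does not give a reason for two different maxima.
- **The most-conservative rule in section 6.5.1.** That rule covers dose adjustments under conflicting toxicity recommendations and does not mention rescue medication. With CRS alone only Table 8 applies, so there is no second recommendation to choose.
- **Meaning of the cap.** Footnote g concerns study-drug dosing, so the analogy is imperfect. The other reading widens the gap.

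It is also fair to say that the protocol does not state that more than 800 mg causes harm, and that the head count above rests on assumed figures.

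**Conclusion.** The concern holds as a minor inconsistency in safety guidance. Above 100 kg, following Table 8 as written gives more tocilizumab per infusion than the ceiling in Table 10: 10% more at 110 kg, 20% at 120 kg and 40% at 140 kg. Up to 100 kg a single infusion is the same under both.

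The 100 kg threshold depends on reading the cap as per infusion. The estimate that fewer than one participant would be affected depends on the assumed weights and rescue rates. Confidence is medium, because the master protocol has not been seen.

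**What to change.** In Substudy 04, Table 8, state the dose as 8 mg/kg to a maximum of 800 mg per infusion, keeping the minimum interval of 8 hours and the limit of four doses. In Table 10, replace the ambiguous limit on total dose with the same maximum of 800 mg per infusion.

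The cost is one line in each of two tables at the next amendment, with no change to conduct, data collection or analysis. The wording should be checked against the master protocol at the same time.
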